5.0 Inclusion and Exclusion Criteria

5.1 **Eligibility screening and retention.** Adult, living patients potentially eligible for the CET based on their current tobacco use status (as recorded in Health Link), a diagnosis of cancer within the past 3 years, receipt of care in a participating cancer clinic in the past year, and not having a preferred language other than English recorded in the EHR, will be identified by UW Health CRDS reports sent securely to UW-CTRI on a quarterly basis through ICTR REDCap.

This list of potentially eligible patients will guide UW-CTRI study coordinators who will first send letters notifying patients that they have been identified as potentially eligible for the CET and Wisconsin Tobacco Quit Line treatment.

The study letters sent to participants will include all required elements of such recruitment tools, and will inform patients that they will receive phone calls inviting them to learn more about smoking treatment options, unless they elect to opt-out of such outreach. The letter will direct patients who wish to opt out of such calls and future mailings to call UW-CTRI to request that they be removed from future outreach efforts. Patients will also have the opportunity to opt out of future outreach at any outreach calls, as well (if they have not already opted out after receiving the letter).

All opt-out requests will be respected throughout the duration of the project. In order to ensure that such opt-outs are respected, we will need to maintain a list of people who opted out until the project ends, as they may appear on future quarterly reports that will guide outreach, and we will need to maintain a cumulative list of patients who opted out to ensure we do not contact them against their stated wishes. This list will need to contain enough information to identify patients (name, phone numbers, date of birth, and MRN), along with their study status (i.e., opted out of all contact). These identifiers will be stripped from the data after the close of recruitment/outreach activities. Basic demographics (age, sex, gender, race, ethnicity) and insurance type will also be collected, and this will be maintained after the close of recruitment/outreach in de-identified manner (i.e., age will be truncated at 90 and recoded into 5-year bins) for analyses

PROTOCOL TITLE: Comparative Effectiveness Trial of Tobacco Cessation Treatments among Cancer Patients who Smoke

of the representativeness of tobacco treatment reach of both Wisconsin Tobacco Quit Line standard care and comparative effectiveness trial treatment.

Recruitment fliers will also be placed in participating clinics and/or distributed by cancer care teams so that patients may proactively contact the study team to learn about tobacco treatment options.

For patients who do not opt-out of tobacco treatment outreach, UW-CTRI study coordinators will make up to 5 phone call attempts to the patient telephone numbers in the EHR over 12 weeks. When a study coordinator reaches a patient, s/he will explain that UW-CTRI is reaching out to patients who smoke and receive cancer care at UW Health/Carbone to offer support and resources, including both standard care (e.g., Wisconsin Tobacco Quit Line referral) and the opportunity to screen for eligibility for a UW-CTRI study.

Patients who are interested in treatment from their care teams or the Wisconsin Tobacco Quit Line (WTQL) (or the quit line in their home state, if outside of Wisconsin) will be given the appropriate referrals. Patients who are interested in the UW-CTRI study will be given a brief description of this study and invited to complete a brief screening for the study (See uploaded Recruitment Call Script) to determine study eligibility.

Please note that being medically eligible to use study medication is not required for study entry. Participants will be screened for medication eligibility if they elect to enter treatment, but participants who are medically ineligible to use study medications will still receive smoking cessation counseling as part of study treatment.

For the one-time qualitative interviews, eligibility criteria are minimal. Participants will be adults with a history of cancer. Past tobacco use is not a criterion for interview eligibility.

Actively declining study participation by notifying the study team that patients would like to be removed from the list of potentially eligible patients will be exclusionary in EHR data extraction. As such, deidentified EHR data will not be gathered from patients who stated they did not want to be included in the study.

5.2 Inclusion criteria. The following criteria will be used to identify patients eligible for initial outreach based on data recorded in Health Link.

- Alive.
- Age 18 years or older.
- Diagnosed with cancer in the past 3 years.

PROTOCOL TITLE: Comparative Effectiveness Trial of Tobacco Cessation Treatments among Cancer Patients who Smoke

- Received care from a participating oncology clinic in the past year.
- Has a current tobacco use status.
- Does not have a preferred language other than English (missing language preference will be included).
- Valid address that is not a correctional facility or residential treatment/care facility.
- No flag for patient cognitive impairment, activated health care power of attorney, or other health care agent (e.g., legally authorized representative) in the EHR.

The following additional inclusion criteria must be met for inclusion in the CET

- Smoked combustible cigarettes in the past month.
- Able to speak and understand English.
- Willing to set a date to quit smoking in the next 60 days.
- Willing to receive smoking treatment information.
- Willing to complete study activities.

For qualitative interviews, the only inclusion criteria are:

- At least 18 years of age.
- Have a history of cancer.
- Willing to participate in an audio-recorded interview about their experiences and perspectives.

5.3 Exclusion criteria. The following exclusion criteria apply to the CET:

- Current suicidal ideation.
- Suicide attempt in the past year.
- Currently receiving treatment for bipolar disorder, schizophrenia, schizoaffective disorder, or psychotic disorder.
- Incarceration.
- Unable to provide informed consent to treatment (i.e., cannot answer questions about study procedures or risks after hearing about the study).

Those who decline the screening invitation or do not meet eligibility criteria will be advised to quit smoking and offered standard smoking cessation treatment (referral to their primary care provider

PROTOCOL TITLE: Comparative Effectiveness Trial of Tobacco Cessation Treatments among Cancer Patients who Smoke

and/or to the Wisconsin Tobacco Quit Line or other tobacco quit line, as appropriate given state of residence).

The only exclusion criterion for qualitative interviews is not being able to provide informed consent due to difficulty understanding the consent information.

5.4 Target populations. We will not target specific subpopulations in the proposed study, but hope instead to enroll a broad and representative sample by reaching out to all adult patients who smoke and meet the prerequisites listed above. The proactive outreach approach to be adapted in this project has increased the reach and equity of smoking cessation treatment in primary care and inpatient contexts (Creswell et al., 2022; [name] et al., 2022). In this approach, proactive outreach regarding smoking treatment options is the default for all adults whose EHR records suggest they currently smoke, unless they opt out of such outreach. Such proactive outreach processes have especially strong reach in historically underserved populations (e.g., African-American, Hispanic, and/or Medicaid-eligible patients; Creswell et al., 2022; [name] et al., 2022) and we anticipate this will hold in population of patients with cancer that will be the focus of this project.

6.0 Special Populations

6.1 Special population inclusion, justification, and safeguards.

- Children/Minors (HRP-416 - CHECKLIST - Children)
- Pregnant persons / fetuses (HRP-412 - CHECKLIST - Pregnant Persons; HRP-413 - CHECKLIST - Non-Viable Neonates; HRP-414 - CHECKLIST - Neonates of Uncertain Viability)
- Prisoners (HRP-415 - CHECKLIST - Prisoners)
- Participants with impaired decision-making capacity (HRP-417 - CHECKLIST - Adults with Impaired Decision-Making Capacity)

Although pregnant persons will be eligible for CET inclusion and smoking cessation counseling, they will not be eligible for any study medication while pregnant or breastfeeding. Quitting smoking has important health benefits for both pregnant persons and their fetuses, so we will not withhold smoking cessation counseling for pregnant persons. We will not dispense study medications during pregnancy or breastfeeding, however, to prevent any adverse effects of medication on fetuses.

We will not target special populations for qualitative interviews. Adult patients with a history of cancer will be referred to the study team if interested in participating in an interview by their cancer care team, without targeting to special populations.

PROTOCOL TITLE: Comparative Effectiveness Trial of Tobacco Cessation Treatments among Cancer Patients who Smoke

6.2 Vulnerable population inclusion, justification, and safeguards.

- Individuals who are receiving inpatient or outpatient services for mental illness, developmental disability, or alcohol and other drug abuse (AODA)
- Individuals who are protectively placed by a court in a treatment facility
- Veterans/Military Personnel
- Emancipated minors
- Anyone especially vulnerable to manipulation or inducements for participation as a result of their illness or socioeconomic condition

We will not target any vulnerable populations in the proposed recruitment strategy, but we anticipate that our broad approach in which proactive outreach regarding smoking treatment is the default will reach members of some special populations, as these populations have especially high smoking rates (e.g., veterans, socioeconomically disadvantaged people, and people with mental health and substance use smoke at higher rates than the general population). We will not assess all special population status (i.e., we will not ask if participants are veterans or ask about current mental health or substance use treatment).

Special and vulnerable populations are disproportionately affected by tobacco use and its devastating effects. As such, we will not exclude them from participation in the study if they meet all other eligibility criteria. We seek to evaluate interventions that will promote abstinence from smoking from the full range of adult smokers receiving oncology care.

Study coordinators will reach out to the PCP (if at UW Health) and UW Health oncologist of patients who consented to the CET to ask them to review the randomly assigned medication regimen, and to disapprove the medication within 5 business days if they have any concerns about study medications for their patients. Study medications will be sent to participants who have provided informed consent for CET participation only after providers have had this opportunity to review and disapprove study medications. Patients whose providers disapprove varenicline, but not patch, will receive nicotine patches (for 2 weeks in the recommended usual care control condition or for 12 weeks in the intensive treatment condition). Patients whose providers disapprove nicotine patches will receive psychosocial treatments, but no study medications.

We will not reach out to patients flagged in quarterly CRDS reports as having cognitive impairment, an active power of attorney for health care, or other active health care agent.

Vulnerable populations will not be targeted for qualitative interviews.

6.3 **Consent considerations in particular populations.** We anticipate recruiting at least some participants from the groups checked below:

- Non-English speaking participants
- Illiterate or Low Literacy participants
- Participants with visual or hearing impairments
- Status Relationship: Individuals with a status relationship with the PI or other study team members (e.g., employees, students, family members)

To avoid enrolling people incapable of consent we will not reach out to patients flagged in quarterly CRDS reports as having cognitive impairment, an active power of attorney for health care, or other active health care agent. Second, an audio version of the letter sent to patients will be available via QR code for patients who would prefer to hear the information about proactive outreach rather than read it. This accommodation is offered to address concerns about low literacy among some patients. In addition, in the CET, we will only include people who speak and understand English so we can obtain informed consent and administer study treatments and surveys orally over the phone. We will use oral means of communication as our primary modality in CET consent, treatment, and assessment procedures. This will be supplemented by a written study information sheet and medication instructions, but all information will be presented orally to eliminate literacy-related barriers to participant understanding. These accommodations will also reduce barriers to understanding or participation among patients with visual impairments. Patients with hearing impairments who have TTY technology will still be able to communicate by phone with study coordinators and smoking cessation counselors, as well.

7.0 Recruitment Methods

7.1 Source(s) of participants.

Prospective participants in the tobacco treatment outreach and CET will be patients identified via health records at UW Health. We will adapt the process that we have used in primary care (IRB protocols 2019-0054, 2019-0939, 2022-0973) that similarly identifies UW Health patients eligible to receive smoking treatment outreach based on health records. As in those studies, patients identified in CRDS reports will receive study recruitment letters and tobacco treatment outreach offering both standard treatment and research participation opportunities unless they opt out of such outreach. This study will focus on adult patients receiving oncology care rather than primary care, however. Fliers will also be placed in participating clinics or cancer care team members may share the flier with patients.

PROTOCOL TITLE: Comparative Effectiveness Trial of Tobacco Cessation Treatments among Cancer Patients who Smoke

Participants in qualitative interviews will be referred by cancer care team members to the research team, if interested in sharing their perspectives and experiences related to cancer. Participants in the CET will be offered the chance to participate in the qualitative interviews following their 12- and 26-week follow up contacts.

7.2 Identification of potential participants. Potential participants in tobacco treatment outreach and the CET will be identified based on private/protected records (medical records) at UW Health. Records will be accessed by requesting CRDS reports regarding eligible patients on a quarterly basis. These reports will be transferred from UW Health to UW CTRI securely via ICTR REDCap to a secure UW-CTRI REDCap database that will guide study coordinator outreach to patients, and track all patients who opt out of future outreach. Patients may also proactively call the UW-CTRI study team to learn more about their treatment options if they see or receive a recruitment flier in their cancer care clinic.

Participants in qualitative interviews will be identified by cancer care providers who will refer interested patients to the study team. The study team will offer all participants who are enrolled in the CET the opportunity to complete the qualitative interview substudy following their 12- and 26-week follow up contacts.

7.3 Recruitment process. Potential tobacco treatment outreach and CET participants will first receive a mailed letter. This letter will inform patients that they have been identified based on their health records for tobacco treatment outreach from UW-CTRI, and will tell them how to opt out of such outreach by calling study coordinators at UW-CTRI. Letters will be sent no more frequently than once per quarter.

Patients who do not opt out of outreach in response to letters will receive up to 5 phone calls per quarter from UW-CTRI study coordinators who will offer tobacco treatment options including both standard care and the CET as available options. Patients can opt out of future outreach at all such phone calls, as well.

Recruitment fliers will also be placed in participating cancer care clinics and/or cancer care providers may give these study invitation fliers to patients interested in participating. These patients may call the study team to learn more about their tobacco treatment options.

Recruitment for qualitative interviews will be conducted by cancer care providers who will have study invitation fliers to give to patients interested in participating. Cancer care providers may also send Health Link InBasket messages to study lead [name] to indicate that the patient is interested and has agreed to receive a call about participating in interviews. In addition, people who are not

PROTOCOL TITLE: Comparative Effectiveness Trial of Tobacco Cessation Treatments among Cancer Patients who Smoke

interested in or eligible for the CET will be asked if they would be interested in participating in the one-time qualitative interview. Participants in the CET will be offered the chance to participate in the qualitative interviews following their 12- and 26-week follow up contacts.

7.4 **Recruitment materials.** The tobacco treatment outreach and CET recruitment letter and an audio version of the recruitment letter is uploaded with the application. These letters will be sent no more frequently than once per quarter during the recruitment period (anticipated to last 2.5 years). The clinic recruitment flier is uploaded with the application.

The script for outreach calls from UW-CTRI study coordinators is also uploaded with the application. Although study coordinators may make up to 5 attempts to reach participants over 12 weeks, this script will be completed only once per quarter with participants.

Participants may be eligible for a new round of call attempts in future quarters if they appear on a subsequent quarterly CRDS report (and have not already opted out of such calls).

The patient flier and template for Health Link InBasket messages to be used in recruitment for qualitative interviews are uploaded with the application. The script that will be used during interview recruitment calls for referred patients and those who decline or do not meet criteria for the CET is also uploaded with the application.

7.5 **Compensation.** Participants who enroll in the CET will receive pharmacotherapy at no cost (if medically eligible) and will be compensated for completing study assessments according to the following schedule: Baseline phone survey (\$50), 8-week phone follow-up (\$50), 26-week phone follow-up (\$50), biochemical verification of abstinence (\$75 via visit to UW-CTRI for carbon monoxide breath test or urinary cotinine test, or mailed saliva sample kit for cotinine testing). As such, the maximum compensation available to participants will be \$225.

Participants in qualitative interviews will be paid \$40 for completing the interview.

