For Aim 3, we hypothesize that the majority of patients assigned to each condition will initiate treatment and will receive at least some counseling and use at least some of the provided medication. We also hypothesize that patient ratings of acceptability and satisfaction will be favorable. We also expect retention, adherence, and satisfaction with treatment to be higher in enhanced care relative to the standard care control condition. We anticipate that the more-intensive treatment, although more costly, will be cost-effective in terms of the incremental cost effectiveness ratio per additional

PROTOCOL TITLE: Comparative Effectiveness Trial of Tobacco Cessation Treatments among Cancer Patients who Smoke

patient who quits smoking, relative to the comparator condition and to other preventive health interventions.

For Aim 4, we are not testing a specific hypothesis. Instead, we are seeking patient input to enhance the acceptability of tobacco treatment outreach and the relevance of smoking cessation counseling for participants in the CET.

For Aim 5, we expect treatment reach to be especially high among historically undertreated populations (including African-American, Medicaid-eligible patients, and those from disadvantaged neighborhoods), and for the effects of enhanced care (vs. the standard care comparator) to be similar across patient subgroups.

3.4 Study endpoints.

Primary endpoints:

1. Reach of smoking treatment, defined as the proportion of eligible patients who initiate evidence-based smoking treatment through the opt-out referral program. (Aim 1)
2. Biochemically verified 7-day point-prevalence abstinence 26 weeks after a target quit date (confirmed by expired carbon monoxide and/or a cotinine urine or saliva sample test). (Aim 2)

Secondary endpoint:

1. Self-reported 7-day point-prevalence abstinence 12 weeks after a target quit date. (Aim 2).

Exploratory endpoints:

1. Treatment acceptability and feasibility indicators including treatment retention (at each treatment contact/milestone) and completion, medication adherence, patient satisfaction, and patient ratings of burden. (Aim 3).
2. Treatment costs from payer and patient perspectives. (Aim 3).
3. Incremental cost-effectiveness ratios for each additional patient who quits smoking with higher-intensity treatment versus lower-intensity treatment. (Aim 4).

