4.0 Number of Participants

4.1 Total number of participants to be accrued. Up to 82 adult participants will be enrolled in the clinical trial by UW-CTRI staff from UW Carbon Cancer Center clinic referrals over 12-30 months. We will continue enrolling within each clinic until we reach saturation in qualitative data analysis of patient interviews (maximum N=32) and until we reach our target enrollment for the CET (N=50).

4.2 Number of participants needed to complete the research procedures. We anticipate that we will engage 12% of participants in some form of evidence-based treatment, and that 50 will enroll in the proposed comparative effectiveness study while another 50 will opt for the Wisconsin Tobacco Quit Line. As such, we anticipate that we will need to reach out to approximately 833 patients who meet criteria to be included on the quarterly CRDS reports that will guide proactive outreach letters and calls. We anticipate that the remaining 733 participants will either opt-out of smoking treatment outreach, will not be reached by the outreach team, will decline tobacco treatment, will elect to pursue treatment via their primary care provider or other means (e.g., over-the-counter) rather than to use formal treatment, or will not complete the treatment enrollment process for other reasons.

Among the 50 participants who enroll in the CET, we will use an intent-to-treat approach to data analyses so that all randomized participants will be included in key analyses of feasibility, acceptability, and abstinence rates, even if lost to follow-up. In primary analyses of abstinence outcomes, missing cases will be treated as still smoking. This will be supplemented by sensitivity analyses under varying assumptions regarding censored data (i.e., that 5%, 10%, or 20% of missing data are abstinent).

For the qualitative interviews, even 2-5 interviews could inform and enhance study methods. We anticipate that we could reach thematic saturation in qualitative data coding with fewer than 32 interviews, and have set 32 as an upper limit for recruitment.

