- Post-quit call 4 (4 weeks after the target quit date).
- Post-quit call 5 (8 weeks after the target quit date).
- Post-quit call 6 (12 weeks after the target quit date).
- Varenicline starting 7 days before the target quit date (0.5 mg once per day for 3 days, 0.5 mg twice per day for 4 days, 1 mg twice per day for 11 weeks), as per the package insert (medication instructions for patients are uploaded with the application). Those who smoke less frequently than daily will not be eligible for varenicline.
 - If patients in high-intensity treatment are ineligible for varenicline (due to contraindications reported at initial medication screening or clinician disapproval of varenicline for the patient), patients will instead be offered 12 weeks of nicotine patch therapy for use starting on the target quit date, at the following dosing schedule:
 - For those who smoke 10 or more cigarettes per day at enrollment, 21-mg patches (week 1-8), 14-mg patches (week 9-10), 7-mg patches (week 11-12).
 - For those who smoke 5-9 cigarettes per day, 14-mg patches (week 1-10), 7-mg patches (week 11-12).
 - For those who smoke 1-4 cigarettes per day, 7-mg patches.
 - Those who smoke less frequently than daily will not be eligible for patches.
 - Those whose clinicians disapprove of nicotine patch therapy for their patients will not receive patches.
- Mailed information about smoking cessation treatments available from the Wisconsin Tobacco Quit Line (or state quit line in patient's state of residence) and SmokefreeTXT, two publicly funded, remotely delivered treatment services available to the general public. These information sheets are uploaded with the application.

11.2 Drug/Device Handling.

- Study medications (nicotine patches, varenicline) will be received at the Center for Tobacco Research and Intervention by the Study Coordinator or designees in the Madison office.
- Nicotine patches will arrive in commercially packaged boxes of 14 patches each (two weeks of 21mg, 14mg, or 7 mg patches).

PROTOCOL TITLE: Comparative Effectiveness Trial of Tobacco Cessation Treatments among Cancer Patients who Smoke

- Varenicline will arrive in commercially packaged 28-day starter packs that clearly designate when and how to start the medication run-in period (beginning 1 week before the target quit day), or 28-day continuation packs (standard commercial packaging sizes).

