Follow-up assessments. UW-CTRI follow-up assessors will call CET participants 12 and 26 weeks after their target quit dates to collect outcome data (see uploaded follow-up surveys) including: tobacco use; quitting motivation and confidence; stress, mood, wellbeing, quality of life, support, and symptom burden; and treatment utilization, satisfaction, and adverse events. In addition to these self-report measures, counseling utilization and medication refill data will be used to track smoking treatment adherence; EHR data on healthcare utilization and diagnoses will be extracted (with patient consent provided at enrollment); and biochemical verification of abstinence claims at the 6-months post-quit follow-up

PROTOCOL TITLE: Comparative Effectiveness Trial of Tobacco Cessation Treatments among Cancer Patients who Smoke

will be obtained via carbon monoxide breath samples and urinary cotinine samples, or mailed saliva samples (as participants are able to provide them).

13.2 CET procedure schedule.

Study Phase	Enroll- ment	Treatment/Intervention Calls								Follow Up Calls	FU Visit
Study Contact	1	2	3	4	5	6	7	8	9	10	11
Week relative to target quit day (tqd, day 0)	-8 to -3	-1	0 tqd	1	2	4	8	12	12	26	26-29
Eligibility screening	✓										
Oral informed consent & HIPAA Authorization	✓										
Clinician(s) given 5 business days to disapprove study medication; medications dispensed if not disapproved	✓										
Tobacco, alcohol, and cannabis history	✓										
Nicotine dependence	✓										
Motivation to quit	✓	✓	✓	✓					✓	✓	
Quitting confidence	✓	✓	✓	✓					✓	✓	
Stress, mood, and withdrawal		✓	✓	✓					✓	✓	
Wellbeing and quality of life	✓								✓	✓	
Social support	✓								✓	✓	
Demographics	✓										
Randomization	✓										
Welcome mailing packet with study information sheet sent	✓										
Standard care (SC) counseling (10-15 minutes)		SC	SC	SC							
Standard care nicotine patch treatment (2 weeks)			SC	SC							
Enhanced care (EC), cancer-specific counseling		EC	EC	EC	EC	EC	EC	EC			
Enhanced care varenicline treatment (12 weeks)		EC	EC	EC	EC	EC	EC	EC			

PROTOCOL TITLE: Comparative Effectiveness Trial of Tobacco Cessation Treatments among Cancer Patients who Smoke

beginning with run-in period 1 week pre-quit followed by 11 weeks at full dose post-quit, as per package insert)										
Recent tobacco, alcohol, and cannabis use								✓	✓	✓
Treatment use								✓	✓	✓
Treatment satisfaction								✓	✓	

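### Section 7.5 pays for an 8-week follow-up that is not scheduled in either arm and lists no payment for the week-12 follow-up that measures the secondary endpoint

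*Combined protocol and SAP*

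**What the plan says.** Section 7.5 (Compensation) states that people who enrol in the comparative effectiveness trial "will be compensated for completing study assessments according to the following schedule". It then lists four items:

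- "Baseline phone survey", $50
- "8-week phone follow-up", $50
- "26-week phone follow-up", $50
- biochemical verification, $75

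The stated maximum is $225. The section makes no distinction between arms and has no week-12 item.

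Section 13.1 (Follow-up assessments) sets different times: "UW-CTRI follow-up assessors will call CET participants 12 and 26 weeks after their target quit dates to collect outcome data". The schedule in section 13.2 agrees, with follow-up calls at contact 9 (week 12) and contact 10 (week 26), then a verification visit at contact 11. Section 13.3 repeats weeks 12 and 26 for all participants. Sections 7.1, 7.2 and 7.3, in the same chapter as the payment list, tie the interview invitation to those two contacts.

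The secondary endpoint in section 3.4 is "Self-reported 7-day point-prevalence abstinence 12 weeks after a target quit date". For missing data, section 4.2 says: "In primary analyses of abstinence outcomes, missing cases will be treated as still smoking".

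One week-8 contact does exist. Section 11.1 lists it for enhanced treatment as "Post-quit call 5 (8 weeks after the target quit date"). It is a counselling call.

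**The concern.** A payment schedule should match the assessments that are actually made. This one attaches $50 to a time point with no assessment and lists nothing for one of the two scheduled follow-up calls. That call is more than a courtesy contact. It supplies the only secondary endpoint, and under section 13.2 it also collects treatment use, treatment satisfaction, wellbeing and quality of life, several of which feed the exploratory comparison of the arms in Aim 3.

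The stake is response at week 12. If staff followed section 7.5 as written, participants would be paid for baseline, week 26 and verification but not for the assessment in between. Under the rule that a missing report counts as smoking, each abstinent person who does not answer that call is recorded as a smoker. Participants would also have been told of a maximum payment that the scheduled assessments cannot deliver.

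**Working it through.** **1. Reproduce the stated maximum.** The inputs are the four amounts in section 7.5.

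$50 + $50 + $50 + $75 = $225

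This equals the stated maximum exactly. The list is therefore closed, with no room for an additional, unlisted week-12 payment.

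**2. Match each paid item to the schedule** (sections 11.1, 13.1, 13.2 and 13.3).

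| Item in 7.5 | Amount | Scheduled assessment |
|---|---|---|
| Baseline | $50 | Contact 1, both arms |
| 8-week phone follow-up | $50 | None in either arm |
| 26-week phone follow-up | $50 | Contact 10, both arms |
| Verification | $75 | Contact 11, for those reporting abstinence |
| (no item) | $0 | Contact 9, week 12, both arms |

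The remaining contacts are counselling calls. Contacts 2 to 4 (weeks -1, 0 and 1) apply to both arms. Contacts 5 to 8 (weeks 2, 4, 8 and 12) apply to enhanced care only. Standard care therefore has no contact at week 8, and enhanced care has a counselling call but no follow-up assessment. The adverse-event row of the 13.2 table is damaged in the text as read, but the call lists in section 11.1 establish the week-8 point without it.

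**3. Could a different starting point explain the 8 weeks?** Section 7.5 does not say what the weeks are counted from. Section 13.2 places enrolment 8 to 3 weeks before the target quit date. Counted from enrolment, the week-12 call falls at 12 + 3 = 15 to 12 + 8 = 20 weeks, which is not 8. Counting from enrolment does not reconcile the two sections.

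**4. What can be earned.**

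- As written, with no week-8 assessment and week 12 unpaid: $225 - $50 = $175, and 175/225 = 78% of the stated maximum. The unattainable part is 50/225 = 22%.
- With the 8-week item relabelled as week 12: $50 + $50 + $50 + $75 = $225, unchanged.
- With the 8-week item kept and a separate $50 added for week 12: $225 + $50 = $275, which would make the stated maximum wrong.

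Only the relabelling agrees with both the schedule and the stated total.

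**5. What non-response does at week 12.** Section 4.3 plans 25 participants per arm. With missing counted as smoking, each abstinent participant lost at week 12 lowers that arm's observed rate by 1/25 = 4 percentage points. A missing payment applies to both arms alike. If it cut response by the same factor r in each arm, independently of abstinence, the observed rates would be r × p1 and r × p2. Both rates and their difference would shrink by r, while the ratio (r × p1)/(r × p2) = p1/p2 would not change. The documents give no expected response rate, so r cannot be filled in.

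**The case against.** The strongest reply is that this is a stale label and nothing more. The schedule has one interim and one final phone follow-up, section 7.5 pays for two phone follow-ups, and the total closes. Reading 8 as 12 resolves everything, and nothing shows a decision to leave week 12 unpaid. That is the likely explanation, although the documents do not say so. It argues for low severity. It does not remove the contradiction, because section 7.5 is current operative text and is the rule by which participants are paid.

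The consent script and information sheet are separate uploads and may already say 12 weeks. This also stands, so the review can ask only for a check.

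The protocol softens the consequence too. It plans sensitivity analyses for missing abstinence data, and section 20.2 accepts that 50 participants are too few to test moderate benefits sensitively.

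Two stronger readings are tempting, and the documents support neither:

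- **Payment to one arm only.** Because only enhanced care has a week-8 contact, a reader might infer that only that arm would be paid then. Section 7.5 pays for assessments and draws no distinction between arms, and the week-8 contact is counselling. Read literally, it pays nobody at week 8.
- **A quantified bias in the treatment effect.** A reader might assume lower week-12 response in standard care, derive a spurious odds ratio, and set it against the predicted 1.50. Any such response gap would have to be invented. It would come from the difference in counselling contact between arms, which remains whether or not week 12 is paid. The 1.50 prediction also concerns abstinence at 26 weeks, and the protocol predicts no odds ratio for week 12.

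**Conclusion.** The inconsistency is real and rests on the text alone. Section 7.5 pays for an assessment that is not scheduled in either arm and omits the week-12 assessment. As written, $50 of the stated $225 cannot be earned and week 12 is unpaid in both arms.

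The effect on the data is a possibility, not a demonstrated bias. It assumes that staff apply section 7.5 literally, that the absence of payment lowers week-12 response, and that the missing-as-smoking rule in section 4.2, which is worded for abstinence outcomes generally, covers the week-12 endpoint. On those assumptions, observed week-12 abstinence would be understated and the other measures taken at that call would be less complete. The documents give no basis for sizing the loss or for expecting the payment error itself to fall more heavily on one arm.

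The primary endpoint is not directly affected, since both the 26-week call and verification are paid without distinction between arms. This is a low-severity internal inconsistency and should not be read as a design decision. Confidence is high for the mismatch itself and limited for any consequence.

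**What to change.** In section 7.5, replace the 8-week label with 12-week, so that the $50 attaches to the phone follow-up at contact 9 in both arms. The amounts and the $225 maximum stay as they are. Check that the consent script and the study information sheet state the same time point, and correct them only if they do not. No separate statement about counselling calls is needed, because section 7.5 already confines payment to assessments.

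The cost is a one-word protocol amendment, plus a matching edit to participant documents if the check shows one is needed. It adds nothing to the payment budget implied by the stated maximum. If the study team did intend an additional week-8 assessment, section 13 would have to schedule it, and both the week-12 payment and the stated maximum would need to be set out afresh. Nothing in the current text suggests that intention.
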